#### **9.7.2.2 General Considerations**

In general, a descriptive analysis is conducted. Categorical variables are summarized with frequencies and percentages. Continuous variables are summarized with mean, standard deviation (SD), median, minimum, and maximum.

#### **9.7.2.3 Missing or Incomplete Data and Lost to Follow-up**

No imputation is to be performed.

#### 9.7.2.4 Descriptive Analysis

##### 9.7.2.4.1 Description of Study Enrollment

All enrolled patients will be summarized in the tree of patient disposition, as described below:

enrollment	XXXX cases	(a%)
	Exclude from safety	XX cases
	Reason)	
	Non received an IP	XX cases
Safety analysis	XXXX cases	(b%)
	Exclude form effectiveness	X cases
	Reason)	
	No effectiveness assessment	X cases
Effectiveness analysis	XXXX cases	(c%)

Percentage of a%, b% and c% (corresponding to enrollment) will be calculated.

##### 9.7.2.4.2 Description of Patient Characteristics

Patient characteristics will be summarized for the following variables.

- Patients demographic: sex (male, female), age(year), the aged ( $\leq 65$  yr,  $> 65$  yr), child ( $\leq 18$  yr), pregnancy (yes, no), current disease (yes, no), height, weight, blood pressure, medical history of disease (all cancers, and other diseases without relation with cancer within the last 2 years), cardiovascular disease, hepatic impairment, renal impairment, ECOG PS, date of diagnosis, ISS stage at study entry, site of metastasis and previous treatment regimens for multiple myeloma or no of previous treatment.
- Concomitant medication

##### 9.7.2.5 Analysis of the Primary, Secondary and Exploratory Endpoint(s)

Analysis for specified endpoints will be conducted as follows:

- Safety endpoint:  
Number of patients, subject incidence\_with adverse events, adverse drug reactions and serious adverse events during the observational period will be calculated and summarized (see [Section 11.1](#) the definition of adverse event, serious adverse event, and other safety findings to be collected).
- Effectiveness endpoint:  
Overall response rate for disease assessment - Patients with confirmed sCR, CR, VGPR, or PR will be considered to have achieved an overall response.

Approved

### 9.7.2.6 Sensitivity Analysis

#### 9.7.2.6.1 Subgroup Analysis

Numbers and percentages of patients with AEs will be provided by patient baseline characteristics (gender, age, etc.), and by special populations (ISS stage, elderly patients, patients with hepatic impairment, patients with renal impairment, regimens (KRd vs Kd), dose, cytogenetics, and other special populations). Effectiveness assessment will be performed equally as well.

#### 9.7.2.6.2 Stratified Analysis

No stratified analysis is pre-planned.

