### **8.3 Exploratory Objective(s)**

The exploratory objective of this study is to identify patients characteristics associated with the safety and effectiveness of Kyprolis®.

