#### 9.7.2.6.3 Sensitivity Analysis for Residual Confounding and Bias

No sensitivity analysis is pre-planned.

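### The exploratory objective looks for characteristics associated with outcome, but the planned one-way tables are not crossed with regimen, so an association that arises through KRd or Kd use cannot be told apart

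*Protocol*

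**What the plan says.** Section 8.3 of the protocol states: "The exploratory objective of this study is to identify patients characteristics associated with the safety and effectiveness of Kyprolis". Section 9.7.2.5 names the exploratory endpoint in its heading, but its text covers only the safety endpoint and overall response.

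The analysis by characteristic is in section 9.7.2.6.1: "Numbers and percentages of patients with AEs will be provided by patient baseline characteristics (gender, age, etc.), and by special populations". The list of special populations includes "regimens (KRd vs Kd), dose, cytogenetics, and other special populations", and for response the section adds "Effectiveness assessment will be performed equally as well". Regimen and dose are therefore separate one-way breakdowns beside the others.

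Section 9.7.2.6.2 reads "No stratified analysis is pre-planned". Section 9.7.2.6.3, headed for residual confounding and bias, reads "No sensitivity analysis is pre-planned". Section 9.9 concedes that confounding cannot be excluded. It answers with cautious interpretation and leaves open whether statistical methods could be applied.

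The study is descriptive, has no hypothesis (7.3, 9.7.2.2) and has no control group (9.1).

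**The concern.** The cohort combines two different exposures. In Tables 1 and 2, both regimens start at 20 mg/m² in Cycle 1. From Cycle 2, within the 24 weeks of follow-up, KRd is at 27 mg/m² and Kd at 56 mg/m². The infusion lasts 10 minutes in KRd and 30 minutes in Kd (9.2.6), and only KRd contains lenalidomide. Regimen follows routine prescribing and is not randomised.

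Suppose patients with a given characteristic receive one regimen more often, and that regimen carries a different risk. A one-way table will then show a difference even if the characteristic makes no difference within either regimen, and a real within-regimen difference can be hidden in the same way. A reader of the re-examination report who sees a higher serious AE percentage in, say, patients with renal impairment could not tell whether it goes with the impairment or with the regimen those patients received. That is the question a reader would bring to a list of associated characteristics.

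**Working it through.** **Does any planned table separate characteristic from regimen?** Section 9.7.2.6.1 gives totals for KRd and Kd, and totals for each level of age, sex, ISS stage, renal impairment and so on. It describes no table of a characteristic within a regimen. Sections 9.7.2.6.2 and 9.7.2.6.3 pre-plan nothing that would supply one.

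**Size of the mixing.** The protocol gives no regimen-specific risks and no regimen shares, so every input here is an assumption. Let r1 and r2 be the risks on the two regimens, the same with or without the characteristic. Let s1 and s0 be the shares on regimen 1 with and without the characteristic. Then:

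- pooled risk with the characteristic = s1·r1 + (1 − s1)·r2
- pooled risk without it = s0·r1 + (1 − s0)·r2
- difference = (s1 − s0)·(r1 − r2)

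Take serious AE risks of 45% and 30%, with no effect of renal impairment within either regimen.

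- Shares 80% and 40%: 0.8×45 + 0.2×30 = 42.0% against 0.4×45 + 0.6×30 = 36.0%. The difference is 0.4×15 = 6 points.
- Shares 70% and 50%: 0.7×45 + 0.3×30 = 40.5% against 0.5×45 + 0.5×30 = 37.5%. The difference is 0.2×15 = 3 points.

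Within each regimen the difference is 0 and the risk ratio is 1, so a regimen-stratified (Mantel-Haenszel) risk ratio is also 1. Conversely, a true within-regimen difference of 6 points in the opposite direction would cancel the first case and leave nothing visible in the pooled table.

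A wider range of assumptions, again with no within-regimen effect:

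| Risk KRd / Kd | Kd share without / with | Pooled risk without / with | Difference |
|---|---|---|---|
| 40% / 50% | 30% / 70% | 43% / 47% | 4 points |
| 40% / 60% | 40% / 60% | 48% / 52% | 4 points |
| 40% / 60% | 30% / 70% | 46% / 54% | 8 points |
| 30% / 60% | 20% / 80% | 36% / 54% | 18 points |
| equal | any | equal | 0 |
| any | equal | equal | 0 |

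**The dose subgroup.** Section 9.2.3.2 excludes regimens outside the approved prescribing information. Under Tables 1 and 2, 27 mg/m² belongs to KRd and 56 mg/m² to Kd. A pooled comparison of those doses is therefore largely KRd against Kd again and cannot separate dose from lenalidomide. This needs no assumption about how physicians choose.

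**Precision within regimen.** The 95% half-width at a 50% rate is 1.96·√(0.25/n): 4.0 points for n = 600 (the minimum in section 9.5), 5.7 for 300, 8.0 for 150 and 11.3 for 75. Within-regimen tables are workable for common characteristics and weak for rare ones.

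**The case against.** The strongest reply is that this need not be confounding. If the characteristic influences which regimen is chosen, regimen lies downstream of it, and the pooled difference is a true description of how often such patients have the event in routine care. Section 8.3 says only associated, not independently or at a fixed regimen. This stands: the crude table is a valid description, and adjustment for regimen answers a different question. It does not remove the ambiguity, because the crude table alone cannot show which of the two a difference reflects.

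Other replies also have weight.

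- A reader might infer that regimen distorts every association. The documents do not support that: the difference is zero whenever regimen shares or regimen risks are equal.
- A reader might infer that stratification is forbidden. The protocol says only that none is pre-planned, and section 9.9 leaves methods open.
- Regimen is not ignored, since KRd versus Kd totals are planned for AEs and for response.
- No section says how regimen is chosen. That age or renal function drives the choice is an assumption.
- The illustrative differences are small against sampling error. With 300 patients in each group, the 95% half-width for 42% versus 36% is 1.96·√((0.42×0.58 + 0.36×0.64)/300) ≈ 7.8 points, and no test is planned.

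It may also be said that such detail belongs in a statistical analysis plan, which is not at hand. For the choice of estimator that is fair. But the protocol is not silent here: it has headings for stratification and for confounding and fills both with none. A later plan that added these analyses would depart from that text.

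**Conclusion.** The point holds in a limited form. An objective to find associated characteristics is served only by one-way percentages over two pooled, non-randomised regimens, with regimen listed but not crossed. Where regimen use and regimen risk both differ, those tables cannot distinguish an association with the characteristic from one that arises through regimen. The size is the product of the two differences: 3 to 6 points in the main illustration, 4 to 18 in the wider non-zero scenarios, and nothing if either difference is absent. All of these rest on assumed risks and shares. The remark on the dose subgroup rests on the protocol's own tables.

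It would go too far to say that the objective cannot be answered at all, since crude associations can be described as planned. The overall incidence of AEs, serious AEs and ADRs, and the overall response rate, are not affected.

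**What to change.** Replace the sentence in section 9.7.2.6.2 with a statement to this effect:

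- The subgroup tables of section 9.7.2.6.1, for AEs, serious AEs, ADRs and overall response, are also shown within KRd and within Kd.
- For the main characteristics (age, sex, ISS stage, cytogenetic risk, renal and hepatic impairment), a regimen-stratified Mantel-Haenszel risk ratio with 95% CI is given.
- The pooled one-way results are crude, descriptive associations.

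A regimen-adjusted regression is optional. Section 9.7.2.3 plans no imputation, so such a model would use complete cases only, and their number should be reported beside it.

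The cost is extra tables. Regimen exposure (9.3.1) and the listed characteristics (9.3.3) are already collected. The downside is wider intervals and small cells in rare subgroups, which should be shown with their CIs.

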#### 9.7.2.6.3 Sensitivity Analysis for Residual Confounding and Bias

No sensitivity analysis is pre-planned.

### 9.7.3 Analysis of Safety Endpoint(s)/Outcome(s)

See [Section 9.7.2.5](#).

## 9.8 Quality Control

Quality control is conducted by checking whether data management operations were conducted based on the standard operation procedures of data management, and all results of quality control, including deviations and their measurements, are documented/reported and deviations are appropriately corrected if they were found.

## 9.9 Limitations of the Research Methods

This is an observational study, so it has a limitation of internal validity and strength of external validity in comparison with an interventional clinical study. Limitations common to this type of study, along with how to reduce errors, are summarized below.

Limitations	How to reduce errors
Missing and incomplete data are unavoidable, because there are some cases that data could not be collected at all evaluation time points, and some patients could be lost to follow-up.	Efforts will be made to collect as complete data as possible and instructions to investigators.
Selection bias, information bias and confounding cannot be excluded.	Selection of participating medical institutions nationwide Analysis results will be interpreted with caution, acknowledging the limitations, whether or not appropriate statistical methods could be applied to address the bias.

## **10. Protection of Human Patients**

### **10.1 Informed Consent**

This study requires the informed consent to collect medical data from patients with Kyprolis treatment in a routine clinical practice.

No investigator may involve a patient in this study unless the investigator has obtained the informed consent of patient.

Before starting this study, informed consent shall be documented by the use of a written consent form and signed and dated by the patient at the time of consent. A copy of the signed informed consent will be given to the patient. The original signed consent must be maintained by the Investigator.

### **10.2 Institutional Review Board (IRB)**

This study will be conducted in accordance with any applicable local regulation, IRB requirement. This study will have the approval of a properly constituted IRB if required prior to the start of the study.

The investigator is responsible for notifying their IRB of safety information/event in scope of expedited reporting if required.

### **10.3 Patient confidentiality**

The Investigator must ensure that the patient's confidentiality is maintained for documents submitted to Amgen Korea.

Patient medical information obtained as part of this study is confidential and must not be disclosed to third parties, except as noted below.

The Investigator/Institution will permit direct access to source data and documents by Amgen, its designee, MFDS and other regulatory authorities. The access may consist of study-related monitoring, audits/regulatory inspection and IRB/MFDS reviews.

Release of study results should be preserved for the privacy of medical information and must be carried out in accordance with applicable local regulation.

## **11. Collection of Safety Information and Product Complaints**

### **11.1 Definition of Safety Events**

#### **11.1.1 Adverse Events**

An adverse event is any untoward medical occurrence in a patient administered a pharmaceutical product(s) irrespective of a causal relationship with this treatment.

Approved

An adverse event can therefore be any unfavorable and unintended sign (including an abnormal laboratory finding, for example), symptom, or disease temporally associated with the use of a product(s), whether or not considered related to the product(s). The definition of an adverse event includes:

- Worsening of a pre-existing condition or underlying disease
- Events associated with the discontinuation of the use of a product(s), (eg, appearance of new symptoms)

It is the investigator's responsibility to evaluate whether an adverse event is related to an Amgen Korea product prior to reporting the adverse event to Amgen Korea.

– Adverse Drug Reaction

An adverse drug reaction (ADR) is a response to a drug, which is noxious and unintended and which occurs at doses normally used and whose causal relationship to the drug cannot be ruled out. A spontaneously reported AE with unknown relationship to the drug is considered as an ADR.

– Unexpected Adverse Drug Reaction

An ADR whose nature, severity, specificity, or outcome is not consistent with the term or description used in the product labeling is considered unexpected.

### 11.1.2 Serious Adverse Events

A serious adverse event is any adverse event as defined above that meets at least one of the following serious criteria:

- is fatal
- is life threatening (places the patient at immediate risk of death)
- requires in-patient hospitalization or prolongation of existing hospitalization
- results in persistent or significant disability/incapacity
- is a congenital anomaly/birth defect
- is an "other significant medical hazard" that does not meet any of the above criteria

A hospitalization meeting the regulatory definition for "serious" is any in-patient hospital admission that includes a minimum of an overnight stay in a healthcare facility.

"Other significant medical hazards" refer to important medical events that may not be immediately life-threatening or result in death or hospitalization, but may jeopardize the patient or may require intervention to prevent one of the other outcomes listed in the definition above. Examples of such events could include allergic bronchospasm, convulsions, and blood dyspraxia, drug-induced liver injury, events that necessitate an

emergency room visit, outpatient surgery, or other events that require other urgent intervention.

### 11.1.3 Other Safety Findings

Other Safety Findings (regardless of association with an adverse event) include:

- Medication errors, overdose, whether accidental or intentional, misuse, or abuse, involving an Amgen product,
- Pregnancy and lactation exposure,
- Transmission of infectious agents,
- Reports of uses outside the terms for authorized use of the product including off-label use,
- Occupational exposure,
- Any lack or loss of intended effect of the product(s)

### 11.1.4 Product Complaints

Product Complaints include any written, electronic or oral communication that alleges deficiencies related to the identity, quality, durability, reliability, safety, effectiveness, or performance of a product or device after it is released for distribution to market or clinic by either Amgen or by distributors and partners for whom Amgen manufactures the material. This includes any drug(s) or device(s) provisioned and/or repackaged /modified by Amgen. Drug(s) or device(s) includes investigational product.

### 11.2 Safety Reporting Requirements

The investigator is responsible for ensuring that safety events (adverse events, product complaints and other safety findings) observed by the investigator or reported by the patient that occur during the pre-determined data collection period (from Initial visit to Last visit) described in [Table 3](#) are recorded in the patient's appropriate study documentation and CRFs.

Serious adverse events and pregnancy cases must be submitted as individual case safety reports to Amgen via the applicable Amgen Safety Reporting Form (paper or electronic form) within 1 business day of investigator awareness.

See [Appendix C](#) for sample Safety Report Form(s), [Appendix D](#) for Additional Safety Reporting Information regarding the adverse event grading scale & criteria for causality assessment used in this study, and [Appendix E](#) for sample Pregnancy and Lactation Notification Worksheets.

The Investigator may be asked to provide additional information for any event submitted, which may include a discharge summary or extracts from the medical record.

Information provided about the event must be consistent with information recorded on study Case Report Forms (CRFs) where safety data also are recorded (eg, Event CRF).

### **11.2.1 Safety Reporting Requirement to Regulatory Bodies**

Amgen will report safety data as required to regulatory authorities, Investigators/institutions, IRBs or other relevant ethical review board(s) in accordance with Pharmacovigilance guidelines and in compliance with local regulations. The Investigator is to notify the appropriate IRB or other relevant ethical review board of Serious Adverse Events in accordance with local procedures and statutes.

## **12. Administrative and Legal Obligations**

### **12.1 Protocol Amendments and Study Termination**

Amgen Korea may amend the protocol at any time. If the protocol is amended, the Investigator has to follow amendments.

## **13. Plans for Disseminating and Communicating Study Results**

The given re-examination period is 6 years from time of product approval and the recruitment period starts from the time of actual product launch. Patients will be followed up until 28 days after last injection of Kyprolis® or the final assessment at 24W after initial prescription of Kyprolis®. For submission of periodic reports to MFDS, interim data summaries will be produced annually although for the first 2 years the report will be provided biannually. Final report will be provided after 6 years.

### **13.1 Publication Policy**

Study result will be submitted for publication as conference abstracts and/or medical journal articles.

Authorship of any publications resulting from this study will be determined on the basis of the International Committee of Medical Journal Editors (ICJME) Recommendations for the Conduct, Reporting, Editing and Publication of Scholarly Work in Medical Journals, which states:

- Authorship credit should be based on (1) substantial contributions to conception and design, acquisition of data, or analysis and interpretation of data; (2) drafting the article or revising it critically for important intellectual content; (3) final approval of the version to be published and (4) agreement to be accountable for all aspects of the work in ensuring that questions related to the accuracy or integrity of any part of the work are appropriately investigated and resolved. Authors should meet conditions 1, 2, and 3 and 4.
- When a large, multicenter group has conducted the work, the group should identify the individuals who accept direct responsibility for the manuscript. These individuals should fully meet the criteria for authorship defined above.

- Acquisition of funding, collection of data, or general supervision of the research group, alone, does not justify authorship.
- All persons designated as authors should qualify for authorship, and all those who qualify should be listed.
- Each author should have participated sufficiently in the work to take public responsibility for appropriate portions of the content.

All publications (eg, manuscripts, abstracts, oral/slide presentations, book chapters) based on this study must be reviewed through applicable company review processes at Amgen Korea and Amgen prior to submission.

**14. Compensation**

Not applicable.

Approved

**Appendix A. List of Stand-alone Documents**

None

Approved

Appendix B. ENCePP Checklist for Study Protocols

Approved

Appendix C. Sample Safety Reporting Form(s)

Approved

## Appendix D. Additional Safety Reporting Information

### Adverse Event severity Scoring system

The NCI Common Terminology Criteria for Adverse Events 4.03 is a descriptive terminology which can be utilized for Adverse Event (AE) reporting. A grading (severity) scale is provided for each AE term [8].

### Relationship to the study product

(1) Certain

An event occurring in a plausible time relationship to use/administration of the drug, and which cannot be explained by concurrent disease or other drugs or chemicals. The response to withdrawal of the drug should be clinically plausible. The event must be definitive pharmacologically or phenomenologically using a re-challenge procedure if necessary.

(2) Probable/likely

An event with a reasonable time relationship to use/administration of the drug, unlikely to be attributed to concurrent disease or other drugs or chemicals, and which follows a clinically reasonable response on withdrawal (re-challenge information not available)

(3) Possible

An event with a reasonable time relationship to use/administration of the drug, but which could also be explained by concurrent disease or other drugs or chemicals. Information on drug withdrawal may be lacking or unclear.

(4) Unlikely

A temporary occurrence which makes a causal relationship to use/administration of the drug improbable, and in which other drugs, chemicals or underlying disease provide plausible explanations.

(5) Conditional/unclassified

An event about which more data are essential for a proper assessment or the additional data are under examination.

(6) Unassessable/unclassifiable

An event which cannot be judged because information is insufficient or contradictory, and which cannot be supplemented or verified.

For the reporting purposes, it is considered that the events assessed 'unlikely' has no reasonable possibility of a causal relationship between the event and Kyprolis®.

